#### **4.2 Outcomes**

- Describe the frequency and duration of lies in ambulance patients and refine the definition of a harmful lie.
- Understand the care trajectory of patients who have fallen with and without a long lie, their health resource use and care outcomes within 12 months of their fall and long lie.
- Improve understanding of morbidity associated with the injury resulting from the fall, and that relating to the long lie.
- Understand how key stakeholders currently manage and mitigate for long lies and where there is variation in practice/understanding that may be harmful
- Understand the patient and carer perspective of long lies, the psychological impact and areas where advice about how to manage a long lie are required

### **5 STUDY DESIGN and METHODS of DATA COLLECTION AND DATA ANALYSIS, SAMPLE and RECRUITMENT**

We propose to undertake a mixed methods study incorporating 7 linked work packages over 27 months.

**WP1: Understand the characteristics and care trajectory of ambulance service patients who have been unable to get up after a fall.**

#### **WP1 - Data collection**

Data from a linked dataset (CUREd+) will be used to describe the characteristics of ambulance service patients who have been unable to get up after a fall and quantify patients' care trajectory and resource use. The CUREd+ dataset incorporates data including 999 ambulance calls, NHS 111 calls, ED, hospital admissions and basic mental health services data from 2017-2023 with additional demographic data (i.e. postcode), medications and prescriptions data, death registry data and improved data from mental health services and ambulance electronic patient record data (Feb 2019 onwards) which will provide a richer understanding of health and social care use.

All YAS ambulance calls for patients who have been unable to get up following a fall over a period of 24 months will be identified (estimated at a minimum of 115,000 cases, with approximately 16,000 having a documented long lie) and use corresponding CUREd+ data from April 2019-March 2023 Twenty-four months' worth of index cases will be provided, enabling a minimum of 12 months' follow up for all cases. This data will be used to understand the incidence of long lies after a fall, where and when they happen and the estimated length of time waiting for an ambulance, using standardised ambulance dataset parameters including time of injury/illness. When time of injury/illness has been completed, this will be considered as the lie start time, acknowledging that self-report may not be accurate. The fields for 'time of call/ incident time' to 'crew arrival at scene' may also be used where time of injury/illness is not available. The condition of the patient upon initial ambulance clinician assessment will be assessed (e.g. estimate hypothermia rates, suspected fracture, frailty, weight etc.).

The resulting dataset will be used to quantify patients' care trajectory and resource use. Outcomes will include: mortality, ambulance service use, ED resource use (tests, re-attendance), hospital resource use (initial length of stay, reattendance), outpatient use (e.g. tissue viability services), discharge location (including escalation of care needs) and any subsequent ambulance re-contact or hospital reattendance. Data on service factors such as ED wait and hospital occupancy will be collected as these may impact on care. This data will enable an understanding of any differences in care trajectories between patients who have had a long lie, and those whose fall did not result in a long lie.

The relationship between length of lie and key outcome variables will be explored using descriptive and visualisation methods. The impact of the length of lie on key outcomes via a series of regression models will be explored (logistic,

Poisson and other), using different definitions of long lie (including the 1 hour NICE definition) and adjusting for appropriate demographic covariates. This will quantify the impact of a long lie on patient health outcomes, and indicate whether 1 hour is the most appropriate threshold to consider a long lie in terms of health outcomes. The analysis will explore the impact of environmental, geographical and seasonal variables on the length of lie to provide an indication of the factors driving the likelihood of a long lie and enable understanding of targets for future interventions that may influence key outcomes.

Due to the period of analysis including the Covid-19 pandemic, analyses will account for Covid-19 in two ways. Firstly, a categorical covariate will indicate whether a covid lockdown was in place nationally at the time of the long lie. Secondly, a continuous variable consisting of the number of Covid hospital beds will indicate the severity of the pandemic at the time of the long lie. Although it is acknowledged that the impacts of covid are likely to be highly complex, this should not differentially affect those who do and do not have a long lie at a given date (although may affect the balance of those groups). To explore this a sensitivity analysis will be performed including the month of the long lie as a covariate. This will allow us to gain an understanding of any change in the effect of a long lie over time, which will indicate any differences associated with covid lockdowns or pandemic severity.

A full Statistical Analysis plan will be developed and submitted to the Study Oversight Group for approval.

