### **WP1 - Analyses**

Length of lie is of interest as both an outcome (under what circumstances is a long lie more likely) and as a predictor of health outcomes and future resource use.

WP1.1 We will provide a descriptive analysis of length of lie, stratified by patient demographics and the characteristics of calls and resulting attendances, including features which have implications for the care trajectory of the patient (e.g. time of day of the call/attendance, seasonality) to examine seasonal pressures. We will explore the relationship between length of lie and key outcome variables using descriptive and visualisation methods.

WP1.2 We will examine the impact of the length of lie on key outcomes via a series of regression models. Key outcomes will include ambulance conveyance (vs see and treat); number of investigations at ED; acute admission to hospital; number of treatments received; discharge to care home or 'step down' or intermediate care; 12-month mortality; number of and time to first readmission within 12 months; number of and time to first unplanned ED attendance within 12 months; number of and time to first NHS 111 call within 12 months. These will consist of logistic, Poisson, and other regression models as appropriate. Key outcomes will be discussed with both the project management group and the PPI group to ensure all potential relevant outcomes have been included.

These analyses will include length of lie as a continuous variable, as a dichotomous variable based on the NICE 1-hour definition of a long lie in logistic regression, and dichotomised based on other possible explanatory thresholds identified in WP1.1. This will quantify the impact of a long lie on patient health outcomes, and indicate whether 1 hour is the most appropriate threshold to consider a long lie in terms of health outcomes.

These analyses will be carried out as adjusted and unadjusted analyses, including appropriate demographic covariates such as age, sex, ethnicity, deprivation indices, care home residence, indications of frailty and/or comorbidities, time of day, season and any key clinical observations recorded by ambulance crew.

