Analysis will provide an estimate of association between length of time lying after a fall and outcomes. However, the assessment of clinical risk undertaken initially will partly determine the length of time left lying after a fall (i.e. ambulance response times may be shorter where a patient has additional risk factors). This means that a confound in terms of fall severity/clinical risk is possible. Since the data is not currently available to assess what analyses may be possible, we planned a cautious associative analysis in the first instance. This will remain the primary analysis; an assessment of clinical risk will be included as a covariate in the analyses where available.

The possibility of additional causal inference methods will be assessed on receipt of the data and if feasible will be undertaken as a supplementary analysis. This may involve the use of matching (although if systematic differences in

clinical severity exist between groups this may reduce sample size dramatically). Alternatively approaches such as the use of instrumental variables may be used (e.g., distance of event from nearest ED may be an appropriate instrument).

WP1.3 Will explore the impact of environmental, geographical and seasonal variables on the length of lie. This will be undertaken with length of lie as a continuous variable in linear regression and as a dichotomised variable based on results from WP1.2. This will provide an indication of the factors driving the likelihood of a long lie. Results from this analysis in context with those from WP1.2 will facilitate an understanding of targets for future intervention in order to address key outcomes.

PPI will discuss definitions of a long lie at the start of the WP to enable their views to feed into the analysis and the variables used, as there may be PPI perspectives that are relevant that have not been documented in the literature. Their views on the parameters of what is a long lie and how this may vary in different contexts e.g. a fall in the home vs a fall outside. This may help inform any scenario analysis. Results will then be fed back to PPI, their views on the findings discussed and different definitions validated. Proposed definitions will then be fed into the workshops (WP7).

Early analyses from WP1 will be used to feed into WPs 3-6.

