### **WP2 - Analysis**

Aggregated, monthly cost data per patient will be modelled using two-part 'hurdle' Gamma regression models, with length of lie as a primary independent variable. Models will explore the influence of length of lie as a continuous and dichotomised variable as described in WP1. The use of monthly cost data as the primary outcome supports estimates of costs associated with length of lie for each month following the index fall event, facilitating an understanding of whether cost differences increase, decrease, or remain stable over the 12 month follow-up period.

A series of models will be developed to explore the influence of length of lie on resource use. Unadjusted models with only length of lie and month number as predictor variables will give a crude estimate of the influence of length of lie. Patient ID will be included as a random effect to account for individual level clustering.

Second, covariate-only models will establish a 'baseline' against which to assess the adjusted influence of length of lie on cost outcomes. These will include demographic data including age, sex, deprivation decile and ethnicity; clinical characteristics including comorbidities; and features of the incidence including time of year, time of day and distance to nearest ED. The precise list of covariates will depend on data quality and learning from WP1.

Finally, fully adjusted models will include length of lie as a main predictor in conjunction with covariates listed above. This will give adjusted estimates of the effect of length of lie. Likelihood ratio tests will compare the adjusted models with the baseline models to determine the impact of including length of lie as a predictor over and above the covariates. The above models will be developed for all healthcare related costs, and separately for costs related to ED attendances, acute admissions, ambulance calls, NHS 111 calls and outpatient costs.

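### WP1 takes the 'time of injury/illness' field as the lie start whenever it is filled in, without requiring that the entry be the time of the fall or testing what happens if it is not

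*Protocol*

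**What the plan says.** The protocol, section 5, WP1 - Data collection, defines the start of the lie: "When time of injury/illness has been completed, this will be considered as the lie start time". The only trigger is that the field is completed. One caveat follows, "acknowledging that self-report may not be accurate". The interval from call or incident time to crew arrival is a fallback; it "may also be used where time of injury/illness is not available".

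Lie length built this way is used throughout the quantitative work:
- In WP1.2 it is the exposure: "These analyses will include length of lie as a continuous variable". It is also dichotomised at 1 hour and at other cut-points, and the results are meant to "indicate whether 1 hour is the most appropriate threshold to consider a long lie in terms of health outcomes".
- In WP1.3 it is the outcome: "This will be undertaken with length of lie as a continuous variable in linear regression", and it is also analysed in dichotomised form.
- In WP2 the monthly cost models are fitted "with length of lie as a primary independent variable".

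The protocol says that a full statistical analysis plan will be written and approved. That plan is not available here. The start-time rule itself is fixed in the protocol.

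**The concern.** The field name covers two kinds of event. For a patient who tripped, the entry is presumably the time of the fall. For a patient who was unwell first and fell later, it could be the onset of the illness. The rule treats both alike.

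Take a hypothetical patient whose illness began 48 hours before the call, who fell 20 minutes before the call and was reached 30 minutes after it. The lie lasted 20 + 30 = 50 minutes. With illness onset in the field, the rule gives 48.5 hours.

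The caveat about self-report concerns an event that is timed imprecisely. It does not cover an accurate time for a different event. An error of this kind only ever lengthens the recorded lie, and it may be commoner in people already ill, whose outcomes differ for other reasons. At stake are the main exposure of WP1 and WP2 and the judgement on whether 1 hour is the right threshold.

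**Working it through.** **1. The plan's own figure.** The protocol expects "estimated at a minimum of 115,000 cases, with approximately 16,000 having a documented long lie". Its Background (1.1) reports that 39% of falls calls were on the floor and that 35% of those had a documented long lie, about 8,000 a year.
- 115,000 × 0.39 × 0.35 = 15,697, and 2 × 8,000 = 16,000. The figure reproduces.
- On-floor cases: 115,000 × 0.39 = 44,850.

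**2. Is the start time checked anywhere?**
- The fallback operates only when the field is empty.
- The alternative definitions of a long lie in WP1 vary the cut-point, not the start.
- WP1's named sensitivity analysis adds calendar month as a covariate.
- Adjustment for frailty, comorbidity, crew observations and clinical risk acts on confounding. It does not correct a misrecorded exposure.

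**3. Dichotomised exposure.** Let q be the share of truly short lies whose entry makes them look longer than 1 hour. The documents give no value, so q is assumed. With 35% truly long:
- false long lies = q × 0.65 × 44,850
- false share of recorded long lies = 0.65q / (0.35 + 0.65q)

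| q | False long lies | False share | Recorded long-lie share |
|---|---|---|---|
| 1% | 292 | 1.8% | 35.7% |
| 5% | 1,458 | 8.5% | 38.3% |
| 10% | 2,915 | 15.7% | 41.5% |

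The base matters:
- If 35% is the recorded share and already contains the error, the false share is q × [0.65/(1 − q)] / 0.35, or 1.9%, 9.8% and 20.6%.
- If 115,000 is read literally as patients unable to get up, the long-lie share is 16,000/115,000 = 13.9%. The false share is then 0.861q / (0.139 + 0.861q), or about 6%, 24% and 38%.

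**4. Direction of bias, unadjusted risk difference at 1 hour.** Let the true risks be r_L (long) and r_S (short), let r_F be the risk in the false long lies, and let P = 1 − false share.

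Observed minus true difference = (1 − P)(r_F − r_L) + [q/(1 − q)](r_F − r_S).

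- If r_F = r_S (non-differential error), the observed difference is P times the true one: 98%, 92% and 84% for q = 1%, 5% and 10%. This is attenuation.
- The sign changes when r_F lies a fraction (1 − P) / [(1 − P) + q/(1 − q)] of the way from r_S to r_L. For q = 1% this is 0.0182/(0.0182 + 0.0101) = 0.64; for 5%, 0.0850/(0.0850 + 0.0526) = 0.62; for 10%, 0.1566/(0.1566 + 0.1111) = 0.58. Above that point the difference is inflated.

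**5. Continuous exposure.** A simulation assumed lognormal lie times with 35% over 1 hour and log-SD 0.8 to 1.2. It lengthened 1% of all records, independently of outcome, and computed cov(true, recorded)/var(recorded), the factor by which a linear slope shrinks.
- Lengthened by 2–24 hours: slope 31% to 73% of its true value.
- Lengthened by 6–72 hours: slope 5% to 23% of its true value.

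A few extreme values therefore do more damage here than at a 1-hour cut.

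**The case against.** The strongest objection is that the premise rests on a field name. The cohort consists of people unable to get up after a fall, so the natural event to record is the fall. The documents do not say how crews fill in the field, how often an illness onset is entered, or how large the gap would be. This stands. A reader might infer that fallers are in fact being scored with hours or days on the floor that did not happen. The documents show only that the rule permits it.

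A reader might also infer that the error inflates the link between lie and harm and pushes the harmful-lie threshold towards longer durations. That is not supported. Non-differential error attenuates, and inflation needs the affected patients to carry sufficiently high risk. Adjustment for frailty, comorbidity and clinical risk would weaken that route. No calculation establishes an effect on the threshold. Nor do the documents support any figure for the share of very long lies that are false, because this would need assumptions about the tail as well as about q.

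It can fairly be said that plausibility limits and sensitivity runs belong in a statistical analysis plan, and that the WP1.1 plots would show a multi-day tail. But the protocol already fixes the start-time rule, and a plan that followed it would keep the rule. Plots may reveal extreme values, but they do not say which are real.

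Finally, switching the rule according to whether the presenting problem is an illness would be unsound. The Background lists pneumonia, hypothermia, dehydration and rhabdomyolysis among the possible complications of a long lie, so an illness label can be a consequence of the exposure. The fix avoids that switch.

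**Conclusion.** The point holds in a limited form. The protocol accepts a field that can hold illness onset as the start of the lie, attaches no condition that it be the time of the fall, and plans no check on that choice. Lie length drives WP1.2, WP1.3, the 1-hour judgement and WP2.

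The size is unknown. The 2% to 16% of recorded long lies that would be false rests on an assumed 1% to 10% of short lies being affected and on 35% being the true long-lie share; the other two bases in the working give larger shares. The slope results also rest on an assumed lie-time distribution and on error unrelated to outcome. The direction of bias in the lie-outcome association is not determined. A possible error of unknown size and sign in the main exposure is reason enough for an inexpensive test, but it is not evidence that the results will be wrong.

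**What to change.** - Amend the start-time rule so that 'time of injury/illness' is the primary lie start only where it is consistent with being the time of the fall. Check it against call/incident time and against any fall time in the ambulance record, if one exists; the protocol names no such field.
- Do not use an illness-type working impression to reclassify patients.
- Treat implausible or ambiguous entries as an interval, with the recorded time as the earliest start and call time as the latest.
- Repeat the WP1.2, threshold and WP2 models with call/incident time to crew arrival as the lower-bound lie length for all cases. The protocol already names these fields.
- Report how many long lies, and how many very long lies, depend on the choice of start.

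The cost is a change of wording, a consistency flag and one extra set of model runs. The drawback is that some cases will have an interval instead of a single lie length.

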Many older people who fall cannot get up off the floor without help but are likely to be triaged as a low priority call (Category 3 or Category 4) in the absence of any apparent life-threatening signs or symptoms. An ambulance response may take time to arrive due to other higher priority calls, with the result that the patients may be on the floor for extended periods of time, experiencing a long lie. People who are unable to get up off the floor after a fall for over an hour may suffer a number of complications, in part due to delayed medical treatment. Complications of a long lie include potential association between long lies and rhabdomyolysis, hypothermia (primary and secondary), pneumonia, pressure injuries, dehydration, muscle and tissue damage, higher risk of admission to hospital and adverse psychological effects as well as subsequent move into long term care. (Blackburn 2022, Kubitza 2022, Fleming 2008, Tinetti 1993, Wongrakpanich 2018, Ryyanen 1992).

Data from YAS January-June 2023 identified 39% of patients from 999 calls triaged with a complaint of falls were on the floor at the time of call and/or crew arrival, 35% of whom had a documented long lie (approximately 8,000 long lies per annum in Yorkshire region). Previous studies have suggested that long lies (typically defined as >1 hour spent on the floor) occur in around 13-30% of cases (Simpson 2014, NHS Overview 2021, Fleming 2008). These long lies have long been a subject of concern but increasing pressure on ambulance services and longer ambulance response times means that patients are being left for increasingly long periods of time, potentially leading to significantly worsened health outcomes. Mean ambulance response times for category 3 and 4 calls have increased from 64 minutes and 90 minutes respectively in 2017/18 to 107 minutes and 139 minutes respectively in Q1 2023/24 (NHS England AQI). Community-based falls response services have recently been implemented to be dispatched to these ambulance calls due to concerns about harm associated with potential delayed response times. (NHS England 2022)

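### The WP1 fallback for a missing fall time measures only the wait after the call, so some true long lies can be analysed as short lies

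*Protocol*

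**What the plan says.** Protocol section 5, WP1 - Data collection, gives two ways to time the lie. The preferred one is: "When time of injury/illness has been completed, this will be considered as the lie start time, acknowledging that self-report may not be accurate". The fallback is that the interval from call or incident time to crew arrival "may also be used where time of injury/illness is not available". The only measurement caveat is the one on self-report. Nothing is said about floor time before the call, and cases timed by the fallback are not marked or set apart.

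WP1 - Analyses enters length of lie as a continuous variable, dichotomised at the NICE 1-hour definition, and dichotomised at other candidate thresholds. The results are to show whether 1 hour is the best cut. WP1.3 makes length of lie the outcome and looks for what drives it. WP2 - Analysis makes it the main predictor of monthly cost.

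WP1 - Analyses also acknowledges that ambulance response may be quicker for patients with additional risk factors.

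**The concern.** Section 1.1 describes a long lie as more than an hour spent on the floor. With a recorded fall time, the variable can measure that. Without one, it measures how long the ambulance took. The two quantities share a column but differ by the whole of the time before the call.

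Three uses are affected:

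- **WP1.2.** The short-lie group takes in patients with a true long lie but a prompt crew. The effect estimate and the apparent threshold both move.
- **WP1.3.** Delay before the call and ambulance delay are mixed in one outcome, although they point to different interventions.
- **WP2.** Cost differences by length of lie inherit the same error.

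In fallback cases the exposure is the response time itself. If higher-risk patients are reached sooner, they tend to be given the shorter recorded lies, so the error is related to prognosis. The planned clinical-risk covariate addresses confounding, but it does not restore the missing floor time. Refining the definition of a harmful lie is a stated objective, so an error here reaches a main output.

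**Working it through.** **1. The identity.** For a patient still on the floor at crew arrival:

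time on floor = (fall to call) + (call to arrival).

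Taken from the call, the fallback keeps only the second term. As an invented example, 180 minutes before the call plus 50 minutes to arrival is 230 minutes on the floor. The fallback records 50, which is short at the 1-hour cut. If call-to-arrival alone exceeds 60 minutes, the long label is right but the duration is still understated.

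**2. The plan's own count.** WP1 - Data collection gives "estimated at a minimum of 115,000 cases, with approximately 16,000 having a documented long lie". Section 1.1 says "39% of patients from 999 calls triaged with a complaint of falls were on the floor at the time of call and/or crew arrival" and that 35% of these had a documented long lie.

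- 115,000 × 0.39 = 44,850 on the floor.
- 44,850 × 0.35 = 15,698, close to 16,000. Per year this is 7,849, close to the stated 8,000.
- 44,850 − 15,698 = about 29,150 on the floor with no documented long lie.

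The figure reproduces only if the 115,000 are all fall calls. WP1 describes them as patients unable to get up, so 44,850 and 29,150 are inferred.

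**3. How often a crew arrives within 60 minutes.** Section 1.1 gives mean category 3 and 4 responses of 64 and 90 minutes (2017/18) and 107 and 139 minutes (Q1 2023/24). Assuming an exponential shape, the share under 60 minutes is 1 − exp(−60/mean):

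| Mean (min) | Share under 60 min |
|---|---|
| 64 | 61% |
| 90 | 49% |
| 107 | 43% |
| 139 | 35% |

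Lognormal shapes with a coefficient of variation of 0.5 to 1.0 give 6% to 63%, so the shape matters.

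**4. Dilution.** Assumed inputs are:

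- f, share with no recorded start: 10% to 50% (not in the protocol);
- q, share of responses under 60 minutes: 35% to 61%;
- h, share of those with enough pre-call time to pass 1 hour: 25% to 75%;
- 65% true short lies among recorded starts;
- true ratio 1.75, the mortality figure cited in section 1.3;
- mislabelled patients carry the average long-lie risk.

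Mislabelled = 44,850 × f × q × h.

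True short lies labelled short = 44,850 × [(1 − f) × 0.65 + f × q × (1 − h)].

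c = mislabelled / (mislabelled + true short lies labelled short).

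Observed ratio = 1.75 / (1 + 0.75c).

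| f, q, h | Mislabelled | True short | c | Observed ratio |
|---|---|---|---|---|
| 0.10, 0.35, 0.25 | 392 | 27,415 | 1.4% | 1.73 |
| 0.30, 0.43, 0.50 | 2,893 | 23,300 | 11.0% | 1.62 |
| 0.50, 0.61, 0.75 | 10,259 | 17,996 | 36.3% | 1.38 |

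The ratio does not depend on the 44,850, which cancels. It does depend on the 65%. On the literal reading that all 115,000 could not get up, that share becomes 1 − 16,000/115,000 = 86.1%, and the three ratios become 1.74, 1.64 and 1.42.

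This formula cannot fall below 1, because it gives mislabelled patients the average long-lie risk. It therefore shows dilution only and does not measure the prognosis-linked part of the bias.

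**The case against.** The strongest reply is that the wording is permissive. The fields may be used, a full statistical analysis plan is promised for oversight approval, and WP1 - Analyses says the data are not yet available to judge what is possible. Flags and sensitivity analyses normally belong in that plan. The same paragraph also wants the time spent waiting for an ambulance, for which call-to-arrival is the right measure. This stands in part: the substitution is allowed, not fixed. But the protocol names the derivation without its main limitation, and a later plan that followed it would carry the bias forward.

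Many fallback cases are also labelled correctly. With mean responses of 107 and 139 minutes, many would pass 1 hour on the wait alone. That limits the size of the problem at the 1-hour cut but does not remove it.

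A reader might infer more than the text supports:

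- **That missing start times are mainly unwitnessed falls with the longest lies.** This is plausible, but the protocol gives neither witness status nor reasons for missingness. Documentation practice could be the cause.
- **That the lie always ends at crew arrival.** Crew arrival is named only in the fallback sentence.
- **That the interval is always a lower bound.** Section 1.1 counts patients who "were on the floor at the time of call and/or crew arrival", in ambulance service data from January to June 2023. Anyone up before arrival could have a lie shorter than the interval. Incident time is also left undefined.
- **That the association would reverse.** Moving 40% of the 16,000 documented long lies (6,400), at an assumed relative risk of 2.5, into a short group of 29,000 gives [(28,000 − 16,000)/9,600] / [(29,000 + 16,000)/35,400] = 0.98. With 99,000 short lies (115,000 − 16,000) it is 1.25 / (115,000/105,400) = 1.15. The reversal needs the inferred comparator and extreme assumed inputs.

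**Conclusion.** The concern holds as a fault in a stated derivation rule. If the fallback is used, patients still on the floor at arrival lose their pre-call floor time. Some true long lies enter the short-lie group, and other durations are understated. The WP1.2 effect and threshold estimates, WP1.3 and WP2 are all exposed, and the protocol states no safeguard.

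The size is unknown because the missing share is not given. The range of 1.73 to 1.38 is an illustration resting on the assumed missing share, response-time shape and pre-call delay, not an estimate. The protocol's own remark on faster response for higher-risk patients means the direction cannot be taken as towards the null. That is a reason for caution; it does not show that the effect would reverse. Nor do the documents show that the longest or unwitnessed lies are the ones mislabelled.

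**What to change.** Amend WP1 - Data collection in section 5 as follows:

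- Hold fall-to-call and call-to-arrival as separate variables, and flag every case with no recorded start.
- For flagged cases still on the floor at arrival, treat length of lie as no less than call-to-arrival: long if that alone exceeds the cut, otherwise unknown, never short.
- Where records show the patient was up before the crew arrived, do not treat the interval as a lower bound.
- Report results for recorded-start cases beside an analysis that includes missing-start cases as a censored or imputed exposure.
- Compare the characteristics and outcomes of the two groups, since restricting to recorded starts may itself select patients.
- In WP1.3, analyse the two components separately. Use call-to-arrival alone only as waiting time for an ambulance.

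The timing fields are ones WP1 already names, so the cost is derivation rules and some added analysis. The downsides are fewer records in the recorded-start analysis and possible selection into it, which the group comparison can describe but not remove.
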